9.4.5.3 Vital Signs

Baseline is defined as the last non-missing value obtained in screening and prior to the first exposure to study drug. Actual values and changes from Baseline in vital signs will be summarized by study day and study time point. All vital sign data will be presented in patient listings.

Vital sign values will be classified according to the clinical significance as determined by the Investigator. The number of participants with a non-missing result, the number and percentage of participants with a non-clinically significant result, and clinically significant result will be summarized by study visit and study time point. If more than one vital sign result is reported per study day and study time point per parameter, the result yielding the most severe classification will be selected for analysis.

Participants with clinically significant vital sign values will be listed. This listing will include all results of the vital sign parameter that was determined by the Investigator to be clinically significant for a participant across study time points.

9.4.5.4 Physical Examination

Abnormal physical examination findings will be listed.

9.4.6 Other Analyses

Other analyses may be added to the SAP as applicable.

9.5 Interim Analyses

Two interim analyses will be performed.

1. The first analysis will be conducted when about 60 participants (40 participants in the RESP301+SOC arm and 20 participants in the SOC arm) have completed the Day 10 assessment. The purpose of this analysis is to evaluate efficacy of RESP301 with the application of a futility criterion based on the results on SpO₂ change from baseline on Day 10. The following futility criterion will be used for this first interim analysis:

If the difference in the percentage of participants with at least a 2% improvement in SpO₂ between both treatment arms is less than 5%, benefit of RESP301 treatment is not expected. For a final decision to stop the study for futility the results on other endpoints will be considered as well.

As no other modification of the study at the time of the first interim analysis is considered, no adjustment of the alpha level is required.

2. The second interim analysis will be conducted after 150 participants (100 participants in the RESP301+SOC arm and 50 participants in the SOC arm) have completed the Day 14 assessment. The purpose of this analysis is the assessment of futility or a sample size re-estimation in case the actual results differ from the original assumptions for the power calculations of the study, related to the percentage of participants meeting the primary endpoint in the control arm and/or the relative treatment benefit achieved in the RESP301+SOC arm compared to the SOC arm.

To account for the multiple testing due to the second interim analysis an adjustment for the type I error alpha will be applied using the Haybittle-Peto approach which would spend one sided alpha=0.0005 at the second interim analysis and leave one-sided nominal alpha of 0.0249 for the final analysis. The futility criterion for the second interim analysis will be based on the conditional power (CP) for the final results based on the assumption that the remainder of the study will follow the same trend as observed in the interim analysis. If CP at the time of the second interim analysis is less than 20% consideration

will be given to stop the study for futility. At the same time sample size re-estimation will be performed to achieve 80% power at the end of the study. The methodology for the adjustment and the procedure to maintain the type I error level will be described in greater detail in the SAP.

Detailed information, including the boundaries futility and characteristics for the sample size re-estimation at the time of the interim analyses will be provided in the SAP and Data Monitoring Committee (DMC) Charter. Further details are also provided in Appendix 5.

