9.2 Sample Size Determination

A total of 300 hospitalized participants with confirmed COVID-19 will be randomized 2:1 to receive RESP301+SOC (200 participants) or SOC alone (100 participants).

The comparison between the treatment arms for the primary endpoint will have approximately 80% power and alpha level 0.025 (one-sided) to demonstrate significant reductions (15% versus 30%) of the primary endpoint between RESP001+SOC and the Control arm (SOC), a 50% relative reduction for the proportion of participants who progress to level >4 (see definition of the primary endpoint).

Two interim analyses are planned (see Section 9.5 for details):

1. The first IDMC interim analysis will take place after the first 60 participants have completed Day 10 of the study to evaluate whether the study can be stopped for futility based on change from baseline in room air SpO₂. For a final decision to stop the study for futility the results on other endpoints will be considered as well.
2. The second interim analysis will take place after 150 participants have completed Day 14 post-randomization based on event rate for the primary endpoint. The purpose of the second interim analysis will be futility as well as a potential sample size re-estimation in case the actual results differ from the original assumptions.

In addition to the review of efficacy data, safety will be assessed at each of the interim analysis by the IDMC. Further details are provided in Appendix 5.

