3. Non-binding DMC guidance for stopping the study for futility at the first interim analysis is stated as:

If the difference in the percentage of participants with at least a 2% improvement in SpO₂ between both treatment arms is less than 5%, a benefit of RESP301 treatment is not expected. For a final decision to stop the study for futility the results on other endpoints will be considered as well.

As the main futility stopping criterion is based on improvement in SpO₂ (and not on the primary efficacy endpoint), this first interim analysis will be “ignored” in these statistical considerations for an adaptive group-sequential design. We may revisit the first interim analysis at a later point in time when more information is available.

4. Non-binding DMC guidance for stopping the study for futility at the second interim analysis stated as:

The futility criterion for the second interim analysis will be based on the conditional power (CP) for the final results based on the assumption that the remainder of the study will follow the same trend as observed in the interim analysis. If CP at the time of the second interim analysis is less than 20% consideration will be given to stop the study for futility.

5. Current DMC guidance for stopping the study for superior efficacy at the second interim analysis is stated as:

To account for the multiple testing due to the second interim analysis an adjustment for the type-I-error probability will be applied using the Haybittle-Peto approach with one sided alpha=0.0005 at the second interim analysis and leave one-sided nominal alpha of 0.0249 for the final analysis.

6. For initial sample size calculation, the following additional assumptions / features from the protocol have been used

- progression probability up to Day 14 for Standard of Care (SOC): 30%

- progression probability up to Day 14 for RESP301+SOC: 15%
- desired power assuming the alternative hypothesis stated above: 80%
- 2:1 randomization

7. Method for adaptation of the sample size based on the second interim analysis data is stated as

A sample size re-estimation will be performed to achieve 80% conditional power at the end of the study. The methodology for the adjustment and the procedure to maintain the type-I-error level will be described in greater detail in an appendix to the protocol. The maximum increase of the sample size will be limited to a total number of 600 randomized subjects.

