10.5.3 Adaptive Sample Size Re-Estimation

Another objective of the 2nd interim analysis is to re-estimate the sample size based on the unblinded interim results.

Proposed procedure at 2nd interim analysis (planned to include approximately 150 subjects)

- unblinded analysis of the primary efficacy endpoint (“progression to level >4 of modified WHO ordinal COVID-19 scale by Day 14” as a binary endpoint)
- calculation of conditional power (CP) given the interim results and calculated by assuming the interim estimates to be the true distribution parameters for the remaining part of the study
 - if $CP < 4\%$: recommend early stop for futility
 - if one-sided p-value < 0.0005 : recommend early stop for superior efficacy
 - if $50\% < CP < 80\%$ and one-sided p-value ≥ 0.0005 :
 - continue the study with an increased total sample size N^* , so that CP with a total of N^* subjects is increased to 80%, same value as the (unconditional) desired power in the study design
 - N^* , however, is limited to 600 (which is twice the original sample size 300)
 - if $4\% \leq CP \leq 50\%$: continue the study without a change in sample size (otherwise, the sample size would need to be increased too much or the maximum sample size of 600 would not be sufficient to come close to a CP of 80%).

The table on the next page illustrated the proposed procedure for a number of possible results observed at the 2nd interim analysis.

Table with examples for the adaptive sample size procedure described above using the Cui/Hung/Wang (CHW) approach using a weighted (fixed weights determined by the stage-wise sample sizes planned at the design-stage) test for the final analysis:

2 nd IA results with n=150 subjects (50 for SOC, 100 for RESP301+SOC)		CP under observed trend for planned 300	Total sample size required for CP 80% under observed trend	CP under observed trend if total sample size capped by 600
15 (30%)	5 (5%)	$p < 0.0005 \rightarrow$ early stop for superior efficacy		
15 (30%)	10 (10%)	99%	Not applicable	Not applicable
15 (30%)	15 (15%)	90%	Not applicable	Not applicable
15 (30%)	18 (18%)	66%	393	Not applicable
15 (30%)	19 (19%)	55%	483	Not applicable
15 (30%)	21 (21%)	34%	[798]	[67%]
15 (30%)	26 (26%)	3.99%	Early stop for futility	
12 (24%)	10 (10%)	92%	Not applicable	Not applicable
12 (24%)	12 (12%)	77%	321	Not applicable
12 (24%)	14 (14%)	54%	498	Not applicable
12 (24%)	15 (15%)	42%	[646]	[77%]
12 (24%)	18 (18%)	14%	[1800]	[31%]

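### The second interim has two incompatible conditional-power rules (Section 9.5 against Appendix 5), and the stated N, power and stopping probabilities were computed under only one of them

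*Protocol*

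**What the plan says.** **Section 9.5** places the second interim at 150 participants (100 and 50) with Day 14 data. Its futility threshold is CP under the observed trend: "If CP at the time of the second interim analysis is less than 20" percent, consideration is given to stopping. It continues: "At the same time sample size re-estimation will be performed to achieve 80% power at the end of the study". It names no range of CP in which N may or may not change, and it refers to Appendix 5 for further details.

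**Appendix 5, 10.5.1**, item 4 repeats the same threshold as non-binding guidance: "If CP at the time of the second interim analysis is less than 20% consideration will be given to stop the study for futility". Item 7 limits the total to 600.

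**Appendix 5, 10.5.2 and 10.5.3** use another rule. The futility criterion in the design table is CP<4%. The procedure recommends stopping below 4%, increases N only when CP is above 50% and below 80%, and caps N at 600. For CP from 4% to 50% the instruction is to "continue the study without a change in sample size (otherwise, the sample size would need to be increased too much".

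The design table that carries CP<4% also carries the operating characteristics: N=300 for 80% power, a futility stop of 70% under no effect and 6% under 30% vs 15%, and an efficacy stop of 10% under 30% vs 15%. Section 9.2 claims "approximately 80% power and alpha level 0.025 (one-sided").

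**The concern.** The committee needs one futility threshold and one re-estimation rule. The protocol gives two of each, and Appendix 5 contains both thresholds. The same interim result can therefore call for different actions, and the committee would have to choose between them with unblinded data in front of it. A choice made then could be challenged as data-driven.

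The protocol also supports its sample size with numbers that describe only one of the rules. A reader of Section 9.5 would take the 6% risk of a futility stop under the planned effect to go with the 20% threshold, and it does not.

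**Working it through.** **Inputs**
- Section 9.2: "A total of 300 hospitalized participants with confirmed COVID-19 will be randomized 2:1", 200 and 100.
- Appendix 5, 10.5.1, item 6: "progression probability up to Day 14 for Standard of Care (SOC): 30" percent; "progression probability up to Day 14 for RESP301+SOC: 15" percent.
- Section 9.5: interim at 150 of 300 (information fraction 0.5), efficacy at one-sided 0.0005 (z = 3.29), final one-sided 0.0249 (z = 1.9617).
- Assumption: no dropout, since none is stated.

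**1. Interim statistic under 30% vs 15%**

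SE = √(0.30×0.70/50 + 0.15×0.85/100) = √0.005475 = 0.0740, so the mean of z₁ is 0.15/0.0740 = 2.027.

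**2. CP thresholds as z-values**

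CP = Φ[(z₁/0.7071 − 1.9617)/0.7071], so z₁ = 0.7071×(1.9617 + 0.7071×Φ⁻¹(CP)).
- 4%: 0.7071×(1.9617 − 1.238) = 0.512
- 20%: 0.7071×(1.9617 − 0.595) = 0.966
- 50%: 0.7071×1.9617 = 1.387

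This formula returns the CP values in the protocol's example table. For 12/50 vs 18/100, z₁ = 0.06/0.0716 = 0.838 and CP = 13.6% (stated 14%). For 10/50 vs 15/100 it gives 10.0% (stated 10%). For 15/50 vs 21/100 it gives 33.6% (stated 34%). The row 12/50 vs 20/100 is an exception: it computes to 4.7% against a stated 2.6%, and 2.6% belongs to 21 events.

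**3. Reproducing the stated figures, then changing the threshold**

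Power = P(z₁ > 3.29) plus the integral, over z₁ from the futility bound to 3.29, of the density of z₁ times 1 − Φ[(1.9617 − 0.7071 z₁)/0.7071 − 2.027].

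| N held at 300, futility enforced | Stated | CP<4% | CP<20% |
|---|---|---|---|
| Futility stop, no effect | 70% | Φ(0.512) = 69.6% | Φ(0.966) = 83.3% |
| Futility stop, 30% vs 15% | 6% | Φ(0.512 − 2.027) = 6.5% | Φ(0.966 − 2.027) = 14.4% |
| Efficacy stop, 30% vs 15% | 10% | 10.3% | 10.3% |
| Power | 80% | 80.0% | 76.0% |
| N for 80% power | 300 | 299.8 | about 332 |

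The stated figures match the CP<4% column.

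**4. Sensitivity to the test variance**

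Binomial simulation with N held at 300 and CP<20% gives 77.4% to 78.0% power with an unpooled test, and 79.0% to 79.5% with the variance of an unstratified Cochran-Mantel-Haenszel test. A pooled normal approximation gives 81.2%, but it would need only 263 participants for 80% power with CP<4%, so it is not the method behind the 300.

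**5. Power with re-estimation (30% vs 15%, weighted Cui/Hung/Wang test, normal theory)**
- Appendix 5 rule (4%, increase for CP 50–80%, cap 600): 81.7%, expected N 289.
- 20% futility with the Appendix 5 zone: 77.7%.
- Section 9.5 read literally (20% futility, increase for CP 20–80%) with cap 600: 81.2%, expected N 312.
- Futility never enforced, N = 300: 81.8%.

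**6. How often the texts differ**
- CP 4–20% (consider stopping, against continue at 300): 14.4% − 6.5% = about 8.0% of trials under 30% vs 15%.
- CP 20–50% (re-estimate, against leave N at 300): Φ(1.387 − 2.027) − 14.4% = 26.1% − 14.4% = 11.7%.
- Together about 20%; under no effect, 13.7% + 8.4% = about 22%.

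In the example table, the rows at CP 14% and 10% continue under Appendix 5 but lie in the consider-stopping range of Section 9.5. The row at CP 34% stays at 300 under Appendix 5 but is re-estimated under Section 9.5. It would need 798 participants for 80% CP and would reach 67% at the cap.

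**The case against.** Several points on the other side are sound.

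- **Status of the texts.** Appendix 5 is worded as a proposal, and Section 9.5 leaves detailed boundaries to the SAP and DMC charter, which are not at hand. Those documents may add detail, but they cannot follow a protocol that prints two thresholds. Appendix 5 is also where Section 9.5 sends the reader, and it holds the only operating characteristics given.
- **Non-binding guidance.** Section 9.5 speaks only of consideration. A reader might infer that the CP 14% and 10% rows are mandatory stops under it; they are not. The committee still needs one trigger.
- **Power.** A reader might infer that 80% power is reached only under the 4% rule. It is not so: power is 81.8% if futility is never enforced and about 81% under Section 9.5 with re-estimation capped at 600. The 76% combines Section 9.5's futility threshold with a fixed N, which is a complete rule in neither text.
- **Cap.** A reader of Section 9.5 alone might infer an unlimited increase. Item 7 of Appendix 5, 10.5.1, sets 600 for the protocol as a whole.
- **Type I error.** Nothing here shows inflation. It is 0.0250 with the weighted test. With the unweighted Chen/DeMets/Lan test and increases over CP 20–80% capped at 600, it computes to 0.0247.
- **Version.** The quoted text is from Amendment 1. Amendment 2 is current, but the file ends before its statistical sections. Its change table lists no change to Section 9.5 or Appendix 5, so persistence is a fair inference and not an observation.

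**Conclusion.** The contradiction stands: 20% against 4% for futility, and re-estimation without a zone against an increase only for CP of 50% to 80%. It affects about one trial in five under the planned effect. The stated N, power and stopping probabilities belong to CP<4%. At CP<20% the chance of a futility stop under the planned effect rises from 6.5% to 14.4%, and under no effect from 69.6% to 83.3%.

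The effect on power depends on what else is adopted: about 76% by the protocol's apparent method with N fixed at 300 and futility enforced, about 77–79% by simulation, and about 81% with Section 9.5's re-estimation capped at 600. These figures assume true rates of 30% and 15%, no dropout and, apart from the simulations, unpooled normal theory. The finding is that the protocol does not say which rule governs and that its figures fit only one; it is not that the trial is underpowered or that type I error is lost.

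**What to change.** State one futility threshold, one re-estimation zone and the cap of 600 in Section 9.5. Use the same text in Appendix 5 (including item 4 of 10.5.1) and the DMC charter, before any unblinded look.

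- **If the Appendix 5 rule is kept** (non-binding CP<4%, increase only for CP above 50% and below 80%, cap 600), the stated figures remain valid. The cost is wording only, with no extra participants.
- **If 20% is kept**, recompute power and stopping probabilities for the whole rule adopted, including re-estimation, and replace the 70% and 6%. Do not simply print 76%. Say also what happens when 80% CP cannot be reached within 600.
- **If N may rise at CP of 50% or less**, specify the weighted Cui/Hung/Wang final test. Section 10.5.4 justifies the unweighted Chen/DeMets/Lan test only because increases are limited to CP above 50%.

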10.5.4 Overall Adaptive Design Performance

Finally, the Cui/Hung/Wang (CHW) approach is compared to the Chen/DeMets/Lan (CDL) approach without pre-defined fixed weights for the final analysis (which is valid as sample size may only be increased if CP (obtained under observed trend) at the second interim analysis exceeds 50%).

All the results below are for the group-sequential design with adaptive sample size re-estimation procedure as described in previous sections and based on 10.000 simulated trials each.

Scenario 1: true progression probabilities are 30% (SOC) and 15% (RESP301+SOC)

Scenario 2: true progression probabilities are 24% (SOC) and 14% (RESP301+SOC)

Scenario 3: true progression probabilities are 30% (SOC) and 10% (RESP301+SOC)

Scenario 4: true progression probabilities are 24% (SOC) and 20% (RESP301+SOC)

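### Section 9.5 says re-estimation is done to reach 80% power; the Appendix 5 rule targets 80% conditional power in a limited zone and leaves power at about 54–58% at 24% vs 14%

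*Protocol*

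**What the plan says.** Section numbers are those of Version 2.0 (Amendment 1), the latest version whose statistical sections are in the text at hand.

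- **Section 9.2:** 300 participants, randomized 2:1, give about 80% power at one-sided 0.025 for 15% versus 30%. Power here is unconditional. The section describes the second interim as serving futility and possible re-estimation if results depart from these assumptions.
- **Section 9.5, item 2:** the interim takes place after "150 participants (100 participants in the RESP301+SOC arm and 50 participants in the SOC arm) have completed the Day 14 assessment". Re-estimation is tied to a control rate or relative benefit that differs from the power calculation. The section defines CP under the observed trend, says that stopping will be considered below 20%, and continues: "At the same time sample size re-estimation will be performed to achieve 80% power at the end of the study".
- **Section 10.5.1, item 7:** the same step is worded differently: "A sample size re-estimation will be performed to achieve 80% conditional power at the end of the study", with a maximum of 600.
- **Section 10.5.3:** the total rises only if CP is above 50% and below 80%. For CP from 4% to 50% the instruction is to "continue the study without a change in sample size". Below 4%, stopping for futility is recommended.
- **Section 10.5.4:** 24% vs 14% is listed as Scenario 2 among the simulated cases.

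**The concern.** Section 9.5 drops the word conditional. Section 9.2 uses power in the ordinary, unconditional sense, so a reader of the main text will understand that if the control rate or the benefit is lower than planned, the trial is re-sized until it has 80% power. Appendix 5 describes no such property. Most trials with a disappointing interim are either left at 300 or stopped.

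What is at stake is interpretation. If the control rate falls in the low or mid 20s, a non-significant result could be read as coming from a trial re-sized to 80% power, when its chance of detecting the effect was little better than even.

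**Working it through.** **Inputs.** Total 300, 2:1 (9.2). Interim at 50 SOC and 100 RESP301+SOC (9.5). One-sided bounds 0.0005 at the interim and 0.0249 at the end (9.5), so z = 3.291 and 1.962. Futility at CP < 4%, increase for CP 50–80%, cap 600 (10.5.3). Final test either weighted (Cui/Hung/Wang, CHW) or unweighted (Chen/DeMets/Lan, CDL).

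**1. Reproduce the protocol's figures.** With equal stage weights and the observed trend:

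CP = Φ(2·z₁ − √2·1.9617) = Φ(2·z₁ − 2.774)

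N* = 150 + 150·k, with k = ((2.774 − z₁ + 0.842)/z₁)²

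Example, 15/50 vs 18/100: z₁ = 0.12/√(0.0042 + 0.001476) = 1.593. CP = Φ(0.411) = 66%. k = (2.023/1.593)² = 1.613, so N* = 392. The protocol prints 66% and 393. Other rows come out at 55%/483, 77%/321, 54%/496 and 50.4%/533 (printed 55%/483, 77%/321, 54%/498 and 50.4%/534). One row, 12 vs 20 events, prints 2.6% where this formula gives 4.7%; this does not affect the point.

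Operating characteristics also agree:

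- Futility stop under no effect: Φ(0.512) = 70% (printed 70%).
- Superiority stop at 30% vs 15%, drift 2.027: 1 − Φ(3.291 − 2.027) = 10% (printed 10%).
- Power at 30% vs 15% without re-estimation: 80.0% on the z-scale (stated 80%); about 81–84% in binomial simulation.

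**2. How often the rule acts at 24% vs 14%.** Drift at 150: 0.10/√(0.24·0.76/50 + 0.14·0.86/100) = 0.10/√0.004852 = 1.436. CP of 4%, 50% and 80% corresponds to z₁ = 0.512, 1.387 and 1.808.

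| Interim CP | Action | Probability (z-scale) |
|---|---|---|
| < 4% | stop for futility | Φ(−0.924) = 17.8% |
| 4–50% | stay at 300 | Φ(−0.049) − 0.178 = 30.3% |
| 50–80% | increase, at most 600 | Φ(0.372) − 0.481 = 16.5% |
| > 80% | stay at 300 or stop for efficacy | about 35% |

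Simulation gives 17%, 27–30% and 17–18% for the first three rows.

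**3. The gain.** In simulation (unpooled, CHW) the total is raised in 18.1% of trials, and success among these goes from 59.9% to 75.8%. Gain: 0.181 × (0.758 − 0.599) = 2.9 points. With the pooled CDL test: 0.170 × (0.751 − 0.624) = 2.2 points.

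An upper bound: if every enlarged trial succeeded, power would be 50.6 + 18.1 × (1 − 0.599) = 57.9% (unpooled, CHW) or 55.1 + 17.0 × (1 − 0.629) = 61.4% (pooled, CHW). This zone cannot bring 24% vs 14% to 80%.

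**4. Unconditional power** (binomial simulation, 300,000 or more trials per setting; ranges cover CHW or CDL and pooled or unpooled variance):

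| True rates | No re-estimation | Appendix 5 rule |
|---|---|---|
| 24% vs 14% | 51–55% | 54–58% (53.5–57.5) |
| 20% vs 10% | 58–64% | 61–66% |
| 25% vs 12.5% | 71–75% | 73–77% |
| 30% vs 15% | 81–84% | 83–85% |
| 30% vs 10% | 98% | 98% |

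**5. Other readings at 24% vs 14%.**

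- Futility at CP < 20% always acted on, increase for CP 50–80%, cap 600: 50–53%.
- Futility at CP < 20% always acted on, increase for CP 20–80%, cap 600: 55.9–58.6%.
- Futility ignored, increase for CP 50–80%, cap 600: 55–60%.
- Futility ignored, every trial below CP 80% enlarged, cap 600: 72–79%.
- The same with no cap: 89–90%. It is about 81–82% if trials showing no benefit at the interim stay at 300, since no sample size gives those 80% CP under the observed trend.

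**The case against.** The strongest reply is that the protocol already says the right thing elsewhere. Section 10.5.1 says conditional power, and 10.5.3 explicitly sets the CP target apart from the unconditional design power. The no-increase zone is disclosed, and the example table prints capped CPs as low as 23%. Section 9.5 refers to Appendix 5, and its sentence comes just after CP is defined. All of this stands, and it limits the matter to wording in the main text. It does not rescue the sentence. Section 9.5 uses CP for futility and then switches to power. Even read as conditional power, the sentence is wrong without the zone, because the rule makes no attempt at 80% for CP from 4% to 50%.

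Some stronger conclusions that a reader might infer are not supported:

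- *That the scenario results were left out.* Section 10.5.4 says they follow, and the same section in Version 1.0 (10.6.4) shows embedded simulation files, one pair for 24% vs 14%. They may simply not have survived text extraction.
- *That no reading reaches 80% at 24% vs 14%.* With no cap and no futility stopping it does. Section 9.5 itself states no cap and makes futility only a consideration. Appendix 5 does not allow that version.
- *That power exceeds 80% only at 30% vs 15%.* Scenario 3, 30% vs 10%, gives 98%.
- *That the design is faulty.* Power below 80% for a smaller effect is normal for this type of rule, and 24% vs 14% is a 42% relative reduction (10/24), not 50%.

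Detailed methodology is deferred to the SAP. That is not at issue here; the point concerns a performance statement printed in the protocol.

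**Conclusion.** Wrong as written. Section 9.5 attributes to the re-estimation a result, 80% power when the assumptions fail, that the operative rule does not deliver. At the protocol's own 24% vs 14%, power is about 54–58%, of which re-estimation contributes about 2–3 points.

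This rests on the Appendix 5 rule being followed, including its futility stop, and on an interim at exactly 50 and 100 participants. Stratification and missing outcomes are not modelled. Changing the futility limit shifts the figure within about 50–60%, so the conclusion does not depend on settling the separate difference between the 20% limit in 9.5 and the 4% limit in Appendix 5. Version 3.0's Sections 9.2 and 9.5 and its Appendix 5 are not in the text at hand. Its change table lists no edit to them, so the wording probably carries over, but this could not be confirmed.

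**What to change.** In Section 9.5, replace the sentence with:

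> If interim conditional power lies in the pre-specified zone (Appendix 5), the total sample size is increased (maximum 600) so that conditional power under the observed trend is 80%; this does not by itself secure 80% unconditional power when the true rates differ from 30% vs 15%.

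Align the purpose statement in Section 9.2. Quote in the text the unconditional power from the simulations that 10.5.4 already reports, at least for 30% vs 15% and 24% vs 14%. A run at 20% vs 10% would be a useful addition, since it keeps the planned 50% relative reduction at a lower control rate.

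The cost is wording plus figures that largely exist already. Sample size and decision rule stay the same. The only downside is a less favourable stated figure.
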